### Child Participants

-Children taking medication will be eligible for screening after the child has been on a stable medication regimen for at least one month (to minimize chance that treatment effects are due to medication and not the proposed program).

-Presence of conditions that are incompatible with this study’s treatment.

-severe visual or hearing impairment,

-severe language delay,

-psychosis,

-Child does not read or speak Spanish (inability to participate in group treatments).

-Child is in an all-day special education classroom. Children in these classrooms are frequently receiving intensive behavior modification programs and assistance such that the teacher consultation component would be expected to require modification for use in these settings.

### Parent and Teacher Participants

-Student of parent/teacher does not meet child inclusion/exclusion criteria above

-Parent or Teacher does not read or speak Spanish (inability to complete assessment measures or participate in group treatments)

**School Clinician Eligibility:** Any school clinician working in the participating Sinaloa school district.

**CHILD PARTICIPANT ELIGIBILITY:** Screening and confirmation of eligibility for youth will follow a three-stage (multiple-gated) procedure.

Stage 1) Involves identification of children by parent self-referral or staff clinicians at each participating school; children must be having academic and social problems related to inattention and/or hyperactivity/impulsivity.

Students who meet first stage entry criteria (e.g., age, grade, mainstream class placement, absence of significant visual or hearing impairment, severe language delay, psychosis, global intellectual impairment, or serious emotional disturbance requiring special education services, per school clinicians and school records, and living with a caretaker who is available to participate in treatment) will be invited to participate in screening.

Stage 2) Next, our program staff will initiate contact with families who self-referred or are referred by the school or referred families can contact our program staff themselves. Families will complete a screening (remote or in-person, depending on their preference) with our program staff about academic, social, and behavioral functioning at school and at home. Questions from the Developmental Family History Form and items from the Child Sympto Inventory-CSI are used to determine sufficient impairment. Parents of children who meet these criteria will be invited to the third stage of screening.

Stage 3) During the final stage, parents complete the CSI, IRS, and Developmental History Form. Teachers also complete the CSI and IRS. After parents and teachers complete rating forms, judgements about eligibility at stage 3 will be made by UCSF program staff based on the interview and ratings provided by teachers and parents. To document ADHD symptom presence, we require six or more inattention symptoms and/or six or more hyperactive-impulsive symptoms endorsed by either the parent or teacher as occurring ‘often’ or ‘very often’. To document cross-situational impairment (and need for home and school treatment), we require impairment in at least one domain on the Impairment Rating Scale by both parent and teacher (score of 3 or greater). Committee on Human Research (CHR)-approved study descriptions are reviewed and families complete consent and assent forms. Those who consent will complete remaining baseline measures. we will then review all available data, including symptom counts and impairment, following DSM-V guidelines. Final determination of eligibility will be based on the child meeting all study criteria as determined by the PI.

**Parent Participant Eligibility:** Must have a child whom meets the above eligibility requirements. The parent must participate in the intervention.

**Teacher Participant Eligibility:** Must have a student whom is participating in the program. The teacher must be willing to participate in the intervention.

We have used these eligibility criteria successfully in the CLS-FUERTE program pilot.

## CONSENT AND ASSENT PROCESS

School clinicians are informed about the study through the school district SEP liaison. When school clinicians express interest, school site meetings are conducted with the school principal, school clinician and other school staff (if requested) to describe the project and obtain principal approval for participation. If approval is obtained, consent forms will be administered to the school clinicians by our staff.

School clinicians approach referred families to explain the project. At this time, students who meet first stage entry criteria will be invited to participate in the screening process to determine eligibility and will provide verbal consent for exchange of information between the school and our program staff.

Families will have the option to complete the consent process over the phone or Zoom video conferencing (using DocuSign to electronically sign the form), at the child's school, or at UAS. Our staff will explain the study and review the consent/assent forms with the family, ensure that the family understands the major points of informed consent, and address any questions. Families will be given as much time as they need to consider participation, and if they prefer to reschedule their appointment to allow for more time to consider, that will be arranged. If more than one parent/guardian has legal custody, reasonable effort will be made to contact the second parent/guardian and gain consent (and such efforts will be documented on the consent form). Minors will complete a simplified assent form. If, after carefully reviewing the study requirements including risks and benefits, the parent wishes to participate but the child does not, the family will not be eligible. Parents will be referred back to the school for assistance with alternative services, if desired.

Once the family has consented our staff will obtain written consent from teachers at their school site or electronically using DocuSign. Teachers will have the option to complete the consent process in-person, over the phone or Zoom video conferencing (using DocuSign to electronically sign the form), at their school, or at UAS.

## ESTIMATED TIME COMMITMENT FOR PARTICIPANTS:

Youth: 6 60-minute sessions and 1-2 30-minute meetings (Total up to 7 hours)

Teachers: 1 1-hour session, 1-2 30-minute meetings, and up to 2-hours to fill out measures (Total up to 4 hours)

Parents: 6 90-minute sessions, 1-2 30-minute meetings, and up to 2-hours to fill out measures (Total up to 12 hours)

School clinicians: 6 60-minute child sessions, 6 90-minute parent sessions, 1 1-hour teacher sessions, up to 16 30-minute meetings, 9 hours of consultation, and up to 2-hours to fill out measures (Total up to 35 hours)

**STATISTICAL METHODS:** We will initially test the web-based CLS-R-FUERTE program in a 3-school open trial by examining if: 1) school clinician fidelity to intervention on the CORS reaches >80% of content delivered and >4 out of 5 quality rating; school clinicians' ratings on the satisfaction questionnaire reach >4 out of 5; school clinicians' ratings on the SUS reach >80%; and school clinicians' evidence based practice skills, knowledge, and attitudes on the KAB improve from pre to post using repeated-measures T-tests; 2) participant session attendance and engagement/adherence ratings reach >4 out of 5 on the CORS with a benchmark of at least 80%; DRC use reaches >3 out of 5 days; and SUS ratings reach >80%; as well as if improvements on youth outcomes improve from pre to post using repeated-measures T-tests. We will conduct analyses in SPSS. 3) Themes from observation and feedback from the open-trial will be incorporated with results above to inform iterative changes to the web-based program after each school.

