**INCLUSION CRITERIA:** The open-trial across 3 schools in the Sinaloa Public School District will include  $N = 3$  School Clinicians (i.e., 1 per school);  $N = 24$  youth with inattention and disruptive behavior (i.e., 8 youth/school);  $N = 24$  parents (i.e., 1 per youth) and  $N = 24$  teachers (i.e., 1 per youth). School Clinicians at the required  $N = 3$  schools are recruited via annual conferences our team has held with the school district describing our preliminary results to-date. To qualify, school clinicians must speak Spanish, be employed as by a participating school, and be willing to engage in the training activities. Youth with attention/behavior concerns in grades 1-5 and their parents/teachers will be recruited via school-wide meetings at each participating school and teacher/school clinician referral. This is a procedure we've used successfully in our previous work in Sinaloa, Mexico. Specifically, we may invite all families and personnel at participating schools to a meet-and-greet. In this meet-and-greet, we introduce our study team and show a brief silent video depicting a youth with inattention and disruptive behavior. Families who identify with the families in the video can self-refer for a program screener with our team. Teachers or school clinicians also may refer families for a program screener with our team. We have used this recruitment strategy successfully in the CLS-FUERTE program pilot. To qualify, youth must demonstrate  $>6$  symptoms of inattention and/or  $>6$  symptoms of hyperactivity/

impulsivity rated by parents or teachers, and >1 domain of impaired functioning, on a screening with our study team). In addition, > 1 parent or caregiver (here-on referred to as “parent”) and > 1 teacher of the youth must speak Spanish and be willing/available to participate in sessions.

**EXCLUSION CRITERIA:** Anyone who does not speak and read Spanish will be excluded, given that all informed consent, measurement, and activity procedures will be conducted in Spanish.

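### Does the 80% attendance benchmark need a stated denominator and a rule for families who stop early?

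*Combined protocol and SAP*

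**What the plan says.** The Statistical Methods open with "We will initially test the web-based CLS-R-FUERTE program in a 3-school open trial by examining if" a list of benchmarks is reached. Item 1 concerns school clinicians and asks whether "fidelity to intervention on the CORS reaches >80% of content delivered and >4 out of 5 quality rating". Item 2 concerns participants and asks whether "participant session attendance and engagement/adherence ratings reach >4 out of 5 on the CORS with a benchmark of at least 80" per cent. Item 3 combines the results with themes from observation and feedback "to inform iterative changes to the web-based program after each school".

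The numbers behind a per-school figure come from two places. The Inclusion Criteria give 24 "youth with inattention and disruptive behavior (i.e., 8 youth/school" and 3 schools. The section on estimated time commitment gives "Youth: 6 60-minute sessions and 1-2 30-minute meetings", "Parents: 6 90-minute sessions, 1-2 30-minute meetings" and "Teachers: 1 1-hour session, 1-2 30-minute meetings".

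No section defines an analysis set, a rule for early stopping or the treatment of missing ratings, and no dropout rate is assumed.

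**The concern.** The sentence in item 2 runs two measures (attendance and engagement ratings) and two thresholds (above 4 of 5, at least 80%) together. The parallel with the fidelity clause suggests 80% for attendance and 4 of 5 for the rating. Even then it is not stated:

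- whether the 80% is a share of scheduled sessions or of participants who reach a target;
- whether families who stop stay in the denominator;
- whether the short meetings count as sessions;
- whether youth, parents and teachers are taken separately.

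Leaving out families who stop raises attendance by construction, because only those who kept coming are measured. Item 3 uses results school by school, where there are only 8 families. The same attendance records could then be reported as meeting or missing the benchmark, depending on a definition chosen after the data are seen.

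**Working it through.** **Inputs.** 8 families per school, 3 schools, so 3 × 8 = 24, which agrees with the stated total. Parents (and youth) have 6 sessions each: 8 × 6 = 48 per school and 24 × 6 = 144 overall. Attendance patterns are not in the documents; those below are assumptions shown over a range.

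**What 80% requires if all enrolled families count.**
- Share of sessions: 0.8 × 48 = 38.4, so 39 of 48 in a school; 0.8 × 144 = 115.2, so 116 of 144 overall.
- Share of families: 0.8 × 8 = 6.4, so 7 of 8; 0.8 × 24 = 19.2, so 20 of 24.

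**Who is counted.** Let N be families, d early stoppers, k sessions attended before stopping, and s sessions attended by each family that stays. Attendance over all enrolled is [s(N − d) + kd]/(6N); among stayers it is s/6.

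| N | s | d | k | All enrolled | Stayers |
|---|---|---|---|---|---|
| 8 | 5 | 1 | 0 | 35/48 = 72.9% | 83.3% |
| 8 | 5 | 1 | 1 | 36/48 = 75.0% | 83.3% |
| 8 | 5 | 1 | 3 | 38/48 = 79.2% | 83.3% |
| 8 | 6 | 1 | 1 | 43/48 = 89.6% | 100% |
| 8 | 6 | 2 | 1 | 38/48 = 79.2% | 100% |
| 8 | 6 | 2 | 2 | 40/48 = 83.3% | 100% |
| 8 | 6 | 4 | 3 | 36/48 = 75.0% | 100% |
| 24 | 5 | 1 | 1 | 116/144 = 80.6% | 83.3% |
| 24 | 5 | 2 | 1 | 112/144 = 77.8% | 83.3% |
| 24 | 6 | 6 | 1 | 114/144 = 79.2% | 100% |

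In one school, a single stopper changes the answer only when the others are already close to the line. With stayers at 90%, one family that attends nothing gives (7 × 6 × 0.9)/48 = 37.8/48 = 78.8%, but one that attends a single session gives 38.8/48 = 80.8%. With full attendance by the rest, two stoppers suffice only if they leave after 0 or 1 session. Over 24 families, with stopping after session 1, it takes 2 stoppers (stayers at 5 of 6) to 6 (stayers at all 6).

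**Share of sessions or of families.** Six families at 6 sessions and two at 2 give (36 + 4)/48 = 83.3% of sessions, but 6/8 = 75% of families attending at least 80%. Seven at 5 and one at 1 give (35 + 1)/48 = 75.0% of sessions, but 7/8 = 87.5% of families (5/6 = 83.3% reaches 80%). The two definitions can disagree in either direction.

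**Pooling participant types.** If two families stop after session 1 and everyone else, including all teachers, attends fully, youth alone give 38/48 = 79.2%. Youth, parents and teachers together have 8 × (6 + 6 + 1) = 104 sessions, and (104 − 2 × 10)/104 = 84/104 = 80.8%.

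**How much a verdict in one school can say.** Exact 95% intervals are 34.9% to 96.8% for 6 of 8 families and 47.3% to 99.7% for 7 of 8. If each family's true chance of being an attender were exactly 80%, the chance of seeing at least 7 of 8 would be 0.503, and of at least 20 of 24, 0.460. A clear definition would not make the per-school verdict informative.

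**The case for a change.** The strongest case for a change is that the gap is real and cheap to close. No section supplies the missing definition, and a few lines would fix it in advance. A stayers-only count is not far-fetched: the Parent Participant Eligibility paragraph makes taking part in the intervention a condition, so a family that leaves could be argued out of the counted set. The level at which results feed into program changes, one school, is also where the figure is most sensitive.

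What stands is that the sentence is unclear and that the arithmetic is right under its assumptions. Three things weaken the rest.

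- The parent condition concerns who may enter; it is not a rule for removing an enrolled family. Attendance is ordinarily counted against what was scheduled, and the plan fixes the enrolled number at 24.
- It is not settled that the 80% is an attendance share at all. Since 4/5 = 80%, it may only restate the rating threshold, and the early-stopper arithmetic would then not apply. On the reading that gives 80% to attendance, the rating has no required share, and the parallel quality and satisfaction items point to a score.
- Item 3 does not call for a pass or fail at each school. It uses results together with observation and feedback, and a team that lost two of eight families would know it whether the summary read 79% or 83%.

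**Conclusion.** No change is needed. This is a gap in wording that a sensible analyst fills, not a rule that gives a wrong result. The benchmark is a descriptive item in an open feasibility trial. The planned t-tests concern clinician skills and youth outcomes, not attendance, and no stopping or continuation rule refers to the 80%. Counting sessions attended against sessions scheduled for the 24 enrolled families, with raw counts by participant type, gives a sound description and lets a reader apply any other definition.

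The size of the effect is limited and conditional. In one school, one early stopper can move the result across 80% if the others attend about 85% to 90% or less. Two can do so with full attendance by the rest only if they leave after at most one session. Over all 24 families, with stopping after the first session, it takes 2 to 6. These figures rest on assumed attendance and timing, on reading the 80% as a share of the 6 sessions, and on leaving the short meetings out of the count.

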**NCT05425966**

**Principal Investigator:** [name] [name] PhD

**IRB Study Title:** Remote School-Home Program to Improve Youth Attention and Behavior in Mexican Students

**IRB #:** 21-34748

**Reference #:** 321420

**Committee of Record:** San Francisco General Hospital Panel

**Most Recent Approval Date:** 08/22/2022

**Pages 2-6 of the current document:** Study Protocol

**Page 6 of the current document:** Statistical Analysis Plan

**STUDY PROTOCOL:** A total of  $N = 24$  youth with inattention and disruptive behavior will participate in a 3-school open-trial evaluating the web-based CLS-R-FUERTE program in the Sinaloa Public School District (i.e.,  $n = 8$  youth/school). Youth with attention/behavior concerns will be recruited via school-wide meetings at each participating school and teacher/school clinician referral. Parents and teachers of youth will provide informed consent and baseline ratings of ADHD/ODD; youth will provide assent; and school clinicians will be tested on their evidence based practice skills. Next, our team will train school clinicians and monitor fidelity, satisfaction and adherence during the 6-week program. Then we will collect post ratings from parents/teachers and test school clinicians again. We will make iterative updates to the program as indicated after observation/ feedback from each school (totaling 3 iterations). School clinicians, parents, and teachers will be compensated \$10 each time they complete ratings (\$20 total). Our team will iteratively update the web-based program and research protocol based on observations and participant feedback.

CLS-R-FUERTE is a 6-week intervention aimed at reducing attention and behavior symptoms in students. The intervention is based on CLS and includes a comprehensive and integrated student, parent and teacher component. Students presenting with attention and behavior problems at school sites without the CLS-R-FUERTE intervention may be referred to the usual care protocol of that school which may include individual therapy, social skills groups or referrals to the community.

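### Paired t-tests drop every child without a post rating, and the plan names no analysis set or method for missing ratings, so the youth result can be biased in either direction

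*Combined protocol and SAP*

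**What the plan says.** **Analysis.** Under STATISTICAL METHODS, the plan will examine whether youth outcomes "improve from pre to post using repeated-measures T-tests. We will conduct analyses in SPSS". It says nothing more about the youth analysis. No section defines an analysis set, a method for missing ratings, an expected dropout or a sensitivity analysis.

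**Data collection.** Under STUDY PROTOCOL, 24 youth (8 in each of 3 schools) take part. Parents and teachers rate them at baseline. After the 6-week program the protocol states: "Then we will collect post ratings from parents/teachers and test school clinicians again". Parents, teachers and school clinicians are paid $10 each time they complete ratings. No section says whether post ratings will be sought when a family stops attending.

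**Attendance.** Under STATISTICAL METHODS, session attendance and engagement are themselves outcomes, with an 80% benchmark.

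**Parent criterion.** It is worded in three ways:
- Parent Participant Eligibility: "The parent must participate in the intervention".
- INCLUSION CRITERIA: at least one parent and one teacher "must speak Spanish and be willing/available to participate in sessions".
- CHILD PARTICIPANT ELIGIBILITY, stage 1: the child lives with a caretaker who is available for treatment.

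The teacher line beside the first of these asks only for willingness.

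**The concern.** A paired t-test works on the difference between two ratings. A child with a baseline rating but no post rating has no difference and drops out, separately for each measure and rater. With no other rule in the plan, children with both ratings become the analysis set by default.

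This matters if the children who are lost differ from those who remain. The raters are also participants in the intervention. Parents are asked for up to 12 hours, and the plan treats their attendance as something to be measured. It is plausible, though not shown, that disengagement and missing post ratings go together. In a single-arm trial, no control group is subject to the same loss and could offset the effect.

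The question of interest is whether the enrolled youth improved. With losses, the planned test answers it only for youth who were rated twice.

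**Working it through.** **Inputs from the documents.** N = 3 schools × 8 youth = 24, which matches the stated total. The test is a paired t-test with one post assessment. The documents give no attrition rate, effect size, SD or pre-post correlation, so everything below rests on assumed values.

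**Case A: loss related to baseline severity.** Assume ratings with SD 1 at both times, pre-post correlation ρ = 0.6, true mean improvement 0.40 SD and a share p = 0.20 without a post rating. Let g be the baseline gap in SD between children who are lost and children who are kept. With ρ below 1, children with severe baseline scores tend to fall further by the second rating, so losing them lowers the mean change among those kept:

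paired estimate = 0.40 − (1 − ρ) × p × g = 0.40 − 0.4 × 0.20 × g = 0.40 − 0.08g

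| g (SD) | Paired estimate (SD) |
|---|---|
| 0 | 0.40 |
| 0.5 | 0.40 − 0.04 = 0.36 |
| 1.0 | 0.40 − 0.08 = 0.32 |
| 1.25 | 0.40 − 0.10 = 0.30 |

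Simulation (n = 24, 20,000 trials per setting, dropout logistic in the baseline score) agrees. The paired mean was 0.40 SD with no link, 0.36 with a slope of 0.5 per baseline SD and 0.29 with a slope of 2.0. The likelihood-based estimate, which keeps children who have only a baseline rating, averaged 0.40 SD in each setting. The spread across trials was 0.20 to 0.21 SD for both methods. At the strong end, the paired bias of about 0.10 SD is roughly half of that spread.

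**Case B: loss related to the unseen outcome.** Assume that the children kept improve by 0.50 SD, that the m children lost do not improve, and that baseline scores do not differ.

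true mean over all 24 = 0.50 × (24 − m)/24

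overstatement = 24/(24 − m) − 1

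| m missing | True mean (SD) | Paired estimate (SD) | Overstatement |
|---|---|---|---|
| 2 | 0.458 | 0.50 | 9% |
| 4 | 0.417 | 0.50 | 20% |
| 5 | 0.396 | 0.50 | 26% |
| 7 | 0.354 | 0.50 | 41% |

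Simulating m = 5 with ρ = 0.6 gave 0.50 SD for the paired estimate and 0.50 SD for the likelihood-based one, against a true 0.396. The mixed model does not correct this kind of loss. Giving the missing children zero change returns 0.50 × 19/24 = 0.396, because that is what this case assumes.

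**Zero change under case A.** There, zero-change imputation multiplies the paired estimate by 0.80, giving 0.80 × 0.40 = 0.32 down to 0.80 × 0.30 = 0.24 SD, against a true 0.40. It is therefore a cautious bound and not a best estimate.

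**The case against.** **Attendance is not the same as having a rating.** Teachers also rate, have only one 1-hour session, and can rate a child whose parent has stopped coming. Ratings are paid for, and the program lasts 6 weeks. Losses may be few, and with none there is no selection. This stands. It is why the point concerns children with both ratings and not families who stayed, and why it is conditional on loss.

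**The eligibility wording.** A reader might infer from the Parent Participant Eligibility line that a family that stops attending becomes ineligible and is removed from the results. The documents do not support that. The line gives no number of sessions and no time point, and it follows directly on the final eligibility decision at screening. The two other statements of the criterion concern willingness or availability at entry. Attendance is an outcome with its own benchmark, which would make little sense if non-attenders were removed. What remains is an ambiguity, sharpened by the teacher line that asks only for willingness.

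**The mixed model is no cure.** This also stands for case B. It corrects loss explained by the observed baseline score and no more.

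**Proportion.** In a 24-child open trial that revises its program after each school, counts, reasons for missing ratings and a simple sensitivity check might seem enough. But the mixed model costs little and gives the paired estimate when nothing is missing.

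**Conclusion.** The point holds as a conditional one. The planned test is a complete-pair analysis, and nothing in the plan says what happens to children without a post rating. If ratings are lost, the youth result applies to children rated twice and may be too small or too large.

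With 20% lost, correlation 0.6 and a true improvement of 0.40 SD, the paired estimate lies between 0.40 SD and about 0.30 SD, depending on how strongly loss follows baseline severity. A likelihood-based estimate holds at 0.40 SD. If instead 5 of 24 are lost and do not improve while the rest gain 0.50 SD, both methods overstate by about 26%. These values are assumptions. The documents fix neither the size nor the direction of any bias, and with no missing post ratings it is zero.

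The parent wording needs reconciling but is not evidence of exclusion after enrolment.

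**What to change.** Under STATISTICAL METHODS:
- Define the youth analysis set as all enrolled youth with a baseline rating on the measure.
- For each outcome and rater, fit a repeated-measures linear mixed model (SPSS MIXED, time as pre/post, unstructured within-child covariance). With no missing ratings it gives the same estimate as the paired t-test.
- Add one sensitivity analysis giving children without a post rating zero change. Present it as a conservative bound, on the understanding that it is conservative only if those children did not worsen on average.
- Report the number of missing ratings by rater, with reasons where known.

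Under STUDY PROTOCOL, state that parent and teacher post ratings will be sought whatever number of sessions was attended.

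Reconcile the parent wording across Parent Participant Eligibility, INCLUSION CRITERIA and stage 1 of CHILD PARTICIPANT ELIGIBILITY, and say whether the criterion applies at entry only.

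The cost is a few sentences, a few lines of SPSS syntax and slightly more analysis work. The reported improvement may come out smaller or larger than the paired t-test would have given.
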